3.2.2 Description

MEL-T01 (“Meliora”), is a digital intervention, a digital therapeutics (DTx) video game, that is installed and operated on a personal computer with a Windows operating system. MEL-T01 implements a closed-loop cognitive training system that looks and feels like an action video game for entertainment. The game is primarily a first-person action video game with puzzle and strategy elements. The player controls the main character in a fictional 3D landscape.

- The game is a single-player game without online features or social interaction with other players.
- The game is free to play and the player cannot make real- or virtual-currency-based purchases in the game.
- The game has 28 levels that the player passes through following a pre-written narrative and unlocking new game features.
- The game’s difficulty is dynamic and adapts to the player's skill level and its changes.

MEL-S01 is derived from MEL-T01 so that the central game mechanics that implement cognitive training are removed. MEL-S01 thus has reduced cognitive training load but remains very similar to MEL-T01, e.g., in terms of action content, progression, and entertainment value (for details, see 3.6.2).

MEL-T01 and MEL-S01 interventions recommend a total of 48 game-play hours during the 12-week intervention period, and at minimum 24 hours during the 12-week intervention period. The subjects are able to play a maximum of 90 minutes per day.

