3.5 Objectives and hypotheses of the clinical investigation

Main objective

The primary objective of this research is to assess the effectiveness of MEL-T01 in reducing MDD symptoms. The subjects are randomised into three research arms (MEL-T01, MEL-S01, and TAU), and their subject health questionnaire (PHQ-9) scores are measured on five occasions (see Table 1).

Research arms

- MEL-T01
- MEL-S01
- TAU

Time intervals

- T0, before subjects in MEL-T01 and MEL-S01 arm begin the active intervention.
- T1, 4 weeks after T0
- T2, 8 weeks after T0

- T3, 12 weeks after T0
- T4, 24 weeks after T0

Primary hypotheses

- MEL-T01 is superior to TAU in alleviating MDD symptoms as measured by the change in subject health questionnaire (PHQ-9) score between time points T0 (before the intervention) and T3 (after a 12-week intervention).
- MEL-S01 is superior to TAU in alleviating MDD symptoms as measured by the change in PHQ-9 score between T0 and T3.
- MEL-T01 superior to MEL-S01 as measured by the change in PHQ-9 score between T0 and T3.

Secondary hypotheses

- In terms of a score change from T0 to T3,
MEL-T01 is superior to TAU,
and MEL-S01 is superior to TAU,
and MEL-T01 superior to MEL-S01 in:
 - reducing depression symptoms as measured by quick inventory of depressive symptomatology (QIDS),
 - reducing rumination as measured by short-version ruminative response scale (RRS),
 - reducing anxiety symptoms as measured by general anxiety disorder (GAD-7),
 - reducing the disability symptoms as measured by sheehan disability scale (SDS),
 - increasing positive emotions as measured by positive valence systems scale (PVSS),
 - and
 - improving well-being as measured by the WHO-five well-being index (WHO-5)
- The effect of the MEL-T01 is mediated by the training dose, as measured by the subject's total game-playing time during the intervention, and evidenced by a positive correlation between MEL-T01 game time and reduction in symptoms as measured by the PHQ-9.
- The effect of the MEL-S01 is mediated by the training dose, as measured by the subject's total game-playing time during the intervention, and evidenced by a positive correlation between MEL-S01 game time and reduction in symptoms as measured by the PHQ-9.

- The effects of MEL-T01 on depressive symptoms as measured by PHQ-9 are mediated by positive game experience as measured by the immersive experiences questionnaire (IEQ).

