3.7.1.2 Clinical questionnaires

The subjects fill questionnaires prior to the intervention (T0), and 4 (T1), 8 (T2), 12 (T3), and 24 (T4) weeks from the beginning of the research. All questionnaires are answered online.

The subject must fill the questionnaires at T0 before they are randomised into one of the three research arms: the intervention doesn't begin before the subject has filled the questionnaires. At T1, T2, T3 and T4, the subjects have two weeks to fill the questionnaire from the beginning of the time point. If the subject doesn't fill the questionnaire within one week, they are followed up with a phone call.

ASSIST-LITE, PCL-5, and BEAQ are filled only once at T0. The state of care questionnaire is filled in T1, T2, T3, and T4. IEQ measures game experience and is filled only after the subject has played the game. Other clinical questionnaires are filled at T0, T1, T2, T3, and T4. (see also Table 5).

The questionnaires include:

- Immersive experiences questionnaire (IEQ)
- Questionnaire regarding their state of care
- Patient health questionnaire (PHQ-9)
- Quick inventory of depressive symptomatology (QIDS-SR16)
- General anxiety disorder questionnaire (GAD-7)
- Positive valence systems scale (PVSS)
- The ruminative response scale (RRS)
- Alcohol, smoking and substance involvement screening test lite (ASSIST-LITE)
- PTSD checklist for DSM-5 (PCL-5)
- Brief experiential avoidance questionnaire (BEAQ)
- Sheehan disability scale (SDS)
- Well-being index (WHO-5)
- 7 item game addiction scale (GAS)

For details when the subjects are asked to fill the questionnaire, see table 5. For the questionnaire descriptions see 3.6.5.1, and for questionnaire content, see Appendix 7 - Data collected in the study.

Table 5: Clinical questionnaires

	Content	Sign up and background questionnaires	T0 Before playing	T1: T0 + 4 weeks	T2: T0 + 8 weeks	T3: T0 + 12 weeks	T4: T0 + 24 weeks
1	Immersive experiences questionnaire (IEQ)			MEL-T01 MEL-S01	MEL-T01 MEL-S01	MEL-T01 MEL-S01	TAU
2	Treatment status -questionnaire			x	x	x	x
3	Patient health questionnaire (PHQ-9)		x	x	x	x	x
4	Quick inventory of depressive symptomatology (self-report) (QIDS-SR16)		x	x	x	x	x
5	General anxiety disorder questionnaire (GAD-7)		x	x	x	x	x
6	Positive Valence Systems Scale (PVSS)		x	x	x	x	x
7	Short-version ruminative response scale (RRS)		x	x	x	x	x
8	Alcohol, Smoking and Substance Involvement Screening Test (ASSIST-LITE)		x				
9	PTSD Checklist for DSM-5 (PCL-5)		x				

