3.7.2 Data-analysis-inclusion criteria and handling of missing data

To be included in the analysis of the primary hypothesis, the subject has to

- Have played the game version A or B at least 24 hours (50% of the recommended 48 hour game time) during the 12 weeks.
- The subjects must have answered all of the PHQ-9 items on both T0 and T2 or T3.

Handling of missing data:

- Primary endpoint evaluation will be based on the comparison of scores acquired ~~at~~ between T0 and T3.
- When the subject has played the MEL-T01 or MEL-S01 for 24 hours, but the T3 PHQ-9 score is missing, we will use the T2 PHQ-9 score.
- If the subject has accumulated ≥ 24 hours of intervention use and then ceased the use, we will use the first PHQ-9 score after the cessation of use.
- Subjects that do not meet these criteria are excluded from the analysis.
- In regards to our secondary hypotheses, missing data are handled similarly.

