3.10.1 Subjects deviations or violations

The majority of human made deviations are mitigated because the majority of the intervention is digital: answering questionnaires as well as playing the game. Wherever possible, we have mitigated the possibility for the subject to deviate from the CIP.

Before the subject is included in the research, they complete the signup process (see 3.7.1.1), first set of clinical questionnaires (see 3.7.1.2), and their MDD diagnosis is confirmed through clinical interview (see 3.7.1.5). Only then the subject is randomised to MEL-T01, MEL-S01, or TAU group, and they are given access to the intervention (for groups MEL-T01 and MEL-S01). Thus we mitigate the risk of the subject not meeting the inclusion/exclusion criteria.

When the subject arrives at T1, T2, T3, and T4, they are emailed the instructions to complete clinical questionnaires. In addition, the reminder to complete the questionnaires is shown to the MEL-T01 and MEL-S01 group in the game, and they are not able to make progress until they have completed the questionnaires. The questionnaires are filled online. If the subject doesn't fill the questionnaires in 7 days from the onset of T1, T2, T3, or T4, they are followed up with a phone call by the CSC.

The subject is recommended to play the game for 48 hours during the 12 week play period. To be included in the sample we require 24 hours of gameplay. When the subject is contacted by the CSC, the CSC has access to the subject total game time and number of weeks played (but they do not know the subject group). If the subject total game time divided by the number of weeks played is less than 2 (the minimum required), the CSC kindly discusses the topic with the subject encouraging them towards reaching 24-48 hours of playing time during the 12 week play period.

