3.11 Accountability

3.11.1 Control of access to the device

Access to the software is only available as long as the digital key is valid. The digital key can be activated and deactivated remotely by the researchers. Only one install is possible with one digital key. Deactivated key prevents launching the software. The researchers can deactivate the subject's key if the subject doesn't follow the researchers instructions. Access to the game requires login to the distribution channel (Steam) and login to the game client itself.

Access to the MEL-T01 and MEL-S01 software is restricted to subjects who have completed the signup pipeline, T0 questionnaires, and gone through the clinical interview by the CSC. After this, the subjects are randomised to one of the three groups.

Whether in TAU, MEL-T01, MEL-S01 group, the access to the training is 12 weeks from the beginning of the intervention. For 2 weeks after the intervention has ended, the access to the training is denied from the user, but they can access the main menu through which they can complete the questionnaire T3 (groups MEL-T01 and MEL-S01) or T4 questionnaire (TAU group).

After the two weeks are over, the access to the software is denied, and the subject can uninstall it from their device. See Table 6 for a detailed outline of the access to the device.

Table 6: Access to the device

Access to the device											
Study arms	T0 (Before playing)	T1: T0 + 4 weeks	T2: T0 + 8 weeks	T3: T0 + 12 weeks	T3 + 2 weeks	T4: T0 + 24 weeks	T4 + 2 weeks.	After T4 + 2 weeks			
MEL-T01 intervention	T0 begins after CSC confirms the subject is eligible to the study. The subject is randomised to one of the three groups.	MEL-T01 intervention				Access to menu only.	No access to the device.				
MEL-S01 intervention		MEL-S01 intervention				Access to menu only.	No access to the device.				
Treatment as usual ("TAU")		Treatment as usual				Access to MEL-T01 or MEL-S01 intervention		Access to menu only.	No access to device.		

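### Section 3.7.2 can set aside an observed T3 PHQ-9 for a T2 or T1 score in the game arms only, so the two game-versus-TAU contrasts may compare different times since baseline

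*Combined protocol and SAP*

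**What the plan says.** Section 3.5 defines the primary comparisons at one time point, for example "MEL-S01 is superior to TAU in alleviating MDD symptoms as measured by the change in PHQ-9 score between T0 and T3". Section 3.7.2 then sets the rules for choosing the score:

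- Inclusion: "The subjects must have answered all of the PHQ-9 items on both T0 and T2 or T3".
- For a subject with 24 hours of MEL-T01 or MEL-S01 play, "but the T3 PHQ-9 score is missing, we will use the T2 PHQ-9 score".
- For a subject who reached 24 hours and then stopped playing, "we will use the first PHQ-9 score after the cessation of use".
- Secondary hypotheses follow the same handling.

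Section 3.7.3 plans a repeated-measures linear mixed model. On play time, section 3.2.2 states: "The subjects are able to play a maximum of 90 minutes per day".

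Four places bear on when the TAU score is taken. Section 3.7.1.2 allows a window in every arm: "At T1, T2, T3 and T4, the subjects have two weeks to fill the questionnaire from the beginning of the time point". Section 3.15.1 places TAU play between T3 and T4. Table 6 in section 3.11.1 gives TAU "Access to MEL-T01 or MEL-S01 intervention" in that period, while the game arms can reach only the menu for the two weeks after T3. Section 3.10.1 says that "the reminder to complete the questionnaires is shown to the MEL-T01 and MEL-S01 group in the game" and that play is blocked until the forms are done. It makes no such statement for TAU.

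**The concern.** A T0 to T3 contrast is interpretable only if T3 means the same thing in each arm. The cessation rule chooses the scoring visit by what a subject did after randomisation, and only in two of the three arms. Where depression eases over time regardless of arm, an earlier score captures less of that improvement, which works against the devices. Scoring soon after play ends also leaves out any later relapse, which works in their favour. The quantity estimated for each device against TAU would then no longer be the week-12 difference stated in the hypotheses, and the secondary endpoints would share the fault.

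The TAU side raises a smaller question of the same kind. If a TAU subject can start playing before returning the T3 form, that score is no longer a score under usual treatment alone.

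**Working it through.** **The plan's own figure.** A two-sample t-test with d = 0.40, two-sided alpha 0.0167 and power 0.80 gives 133 per arm (power 0.803), as in section 3.7.4.1. The sample size is not in dispute; d = 0.40 serves below only as a yardstick.

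**How early a game-arm score can be.** Inputs: the 24-hour threshold (3.7.2), the 1.5-hour daily cap (3.2.2), the recommended 4 hours per week (synopsis), and T1, T2, T3 at weeks 4, 8, 12 (3.5).

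- At the cap: 24 / 1.5 = 16 days, before T1 at day 28. A subject who then stops is scored at T1, 8 weeks early.
- Reaching 24 hours by T1 needs 24 / 4 = 6 hours per week, above the recommendation.
- At 4 hours per week: 24 / 4 = week 6. A subject who then stops is scored at T2, 4 weeks early.

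Inclusion requires T2 or T3 to be answered, so every included subject scored at T1 also has a later score, possibly T3 itself. In that case the rule imputes nothing; it swaps a later observation for an earlier one.

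**Illustrative size.** The documents give neither the share who stop nor the course of PHQ-9. Assumptions: a linear fall of X = 4 points over 12 weeks in every arm, no device effect, SD 5, and a share f of analysed game-arm subjects scored at week w.

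Shift = f × X × (12 − w) / 12

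| f | scored at T2 (w = 8) | scored at T1 (w = 4) |
|---|---|---|
| 10% | 0.13 points (0.03 SD) | 0.27 points (0.05 SD) |
| 25% | 0.33 points (0.07 SD) | 0.67 points (0.13 SD) |
| 40% | 0.53 points (0.11 SD) | 1.07 points (0.21 SD) |

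For example, 0.25 × 4 × 4 / 12 = 0.33, and 0.33 / 5 = 0.07 SD. With SD 5 the design effect is 0.40 × 5 = 2.0 points, so the 25% row is about a sixth (T2) or a third (T1) of it. These figures show only the loss of common improvement, which makes the game arm look worse. The documents contain nothing from which to size the opposite effect of hidden relapse.

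**Possible TAU exposure before the T3 form.** Access lasts 12 weeks (3.11.1) and T4 is at week 24, so TAU access opens at 24 − 12 = week 12, that is, at T3. The form may come back over the next 14 days:

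- at the recommended rate, 2 weeks × 4 = 8 hours;
- at the daily cap, 14 × 1.5 = 21 hours, which is a ceiling.

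**The case against.** The best defence is that the cessation bullet stands under the missing-data rules, after a bullet that fixes the primary endpoint at T0 to T3, and so may be meant only for subjects without T3. That is a fair reading of the intent, but the wording carries no such condition. The revision history also says that version 2.3 clarified this section to reflect use time, which fits a deliberate rule. Read as applying only to missing T3, the bullet would conflict with the T2 bullet for anyone who stopped before T1. T2 scoring limited to players would remain in either case.

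Several stronger readings are tempting and are not supported:

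- *That T1 scoring contradicts the T2-or-T3 bullet.* That bullet decides who is analysed, not which score is used. A subject can satisfy it and still be scored at T1.
- *That TAU is denied the T2 substitution.* The substitution is worded for players, but a TAU subject with only T2 appears to meet the questionnaire condition, and no score is named. TAU handling is unspecified.
- *That all three primary contrasts are distorted.* MEL-T01 and MEL-S01 follow identical rules. Their comparison is affected only if stopping differs by device.
- *That a quarter of subjects will be scored at T1, or that TAU subjects will play 21 hours before answering.* The first is an assumption and requires play above the recommended rate. The second needs maximum play every day and a form returned on the last day, despite the phone follow-up after one week. Payment rises from 50€ at 24 hours to 120€ at 48 hours, with all questionnaires answered in both cases, which discourages stopping at the threshold.

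It also stands that section 3.10.1 leaves open whether the in-game lock applies once TAU subjects enter the game. TAU exposure before the T3 score is possible on the text, not established.

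**Conclusion.** The cessation rule is wrong as written and should be changed before the primary analysis. It lets an observed T3 score be discarded, in the game arms only, for a score taken 4 or 8 weeks earlier. The two game-versus-TAU contrasts, and the secondary endpoints handled in the same way, can therefore differ in time since baseline. On the stated assumptions, with 10% to 40% of game-arm subjects affected, the shift is 0.13 to 0.53 points for T2 scoring and 0.27 to 1.07 points for T1 scoring. The true share is unknown, partly because the plan does not define when use has ceased, and the net direction cannot be determined from the documents.

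The TAU exposure point is secondary. The sections leave room for it but do not show that it occurs. Any such play would tend to shrink the game-versus-TAU difference if the game works.

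**What to change.** In section 3.7.2, delete the cessation rule and the T2-for-T3 substitution. Use the observed T3 PHQ-9 for every subject who has one, whether or not play stopped. Let the mixed model already planned in section 3.7.3 take in T1 and T2 at their own times, with the arm difference at T3 as the primary contrast. A missing T3 is then handled by the same rule in all three arms, including TAU subjects with T2 only. Apply the same wording to the secondary endpoints. The cost is a wording change in the plan and no new data. The model does rely on T3 being missing at random given the earlier scores, and the plan should say so.

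For TAU, reconcile sections 3.7.1.2, 3.10.1, 3.11.1 and 3.15.1 so that the T3 score is taken before game exposure. How to do so is for the sponsor, since the 12-week access period and T4 at week 24 are also fixed. Report TAU play time logged before T3 submission, and add a sensitivity analysis that excludes TAU T3 scores given after play began. Section 3.6.6.2 says that game data are time-stamped, so this is possible for subjects already enrolled. The exclusion itself depends on behaviour after randomisation, so it should remain a sensitivity analysis.

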3.7.3 Hypothesis tests and multiple comparisons

Primary and secondary objectives in this clinical study are to demonstrate a statistical difference on outcome measure mean change scores between the following groups:

1. MEL-T01 and MEL-S01
2. MEL-T01 and TAU
3. MEL-S01 and TAU

We will first assess whether we use a parametric or non-parametric test.

- Using the Shapiro-Wilk test we explore if MEL-T01, MEL-S01, and TAU model residuals are normally distributed regarding PHQ-9.
- Using Levene's test we test whether the variance of MEL-T01, MEL-S01 and TAU model residuals are equal regarding PHQ-9.
- If both tests are $p > 0.05$, we will use a repeated measures Linear Mixed Model; If either test is $p < 0.05$, we will use a repeated measures Linear Mixed Model with robust standard errors.
- For primary endpoint evaluation (PHQ-9), we will conduct a one-tailed test for the arm pairs MEL-T01-vs.-MEL-S01, MEL-T01-vs.-TAU, and MEL-S01-vs.-TAU. We

are using a significance level of 0.05. Using Holm-Bonferroni correction, we find the multiple-comparison corrected $p = 0.05/3 = 0.0167$.

Change scores are defined as the scores obtained between the pre-intervention (T0) assessment and the during/post-intervention assessments. The general formulation of the null and alternative hypotheses are

$$H_0: \mu_x = \mu_y$$

$$H_1: \mu_x \neq \mu_y$$

where H_0 is the null hypothesis, H_1 is the alternative hypothesis and $x, y \in \{A, B, TAU\}$, $x \neq y$.

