3.1.6 Synopsis of the clinical investigation

Name of sponsor/company: Aalto University
Study identification code: MelioraRCT
Title of the study: The effects of videogames on depression symptoms and brain dynamics
Study period: Planned first subject visit: 1.3.2022. Planned study completion: 31.12.2023.
Participating countries and number of sites: Neuroscience Centre, HiLIFE, University of Helsinki, Finland. Department of Neuroscience and BioEngineering Aalto University, Finland. BioMag laboratory, HUS Medical Imaging Centre, Helsinki University Hospital, Finland. Aalto NeuroImaging Infrastructure, Espoo, Finland
Number of subjects: Main study: $N = 800$ with major depressive disorder (MDD). In addition, in the sub-study: $N = 100$ healthy adults

Study objectives:

The study is a comparator-controlled, randomised, double-blinded intervention study aimed at assessing the effects of the investigational device MEL-T01, “Meliora”, on the symptoms of major depressive disorder (MDD). MEL-S01 acts as a comparator. MEL-T01 is a game-based digital-therapeutics (DTx) medical software device developed at Aalto University and is intended to be used as a treatment for MDD together with treatment-as-usual (TAU). MEL-T01 implements personalised cognitive training to alleviate MDD symptoms and improve cognitive performance in MDD subjects.

Arms and interventions:

Arm	Intervention
MEL-T01	Active investigational device MEL-T01 is a digital intervention implemented in a video game with cognitive training components. MEL-T01 is provided together with Treatment As Usual (TAU).
MEL-S01	Active comparator device MEL-S01 is a digital intervention implemented in a video game with reduced cognitive training load. MEL-S01 is provided together with TAU.
TAU	No intervention.

Primary hypotheses:

- MEL-T01 is superior to TAU in alleviating MDD symptoms as measured by the change in subject health questionnaire (PHQ-9) score between time points T0 (before the intervention) and T3 (after a 12-week intervention).
- MEL-S01 is superior to TAU in alleviating MDD symptoms as measured by the change in PHQ-9 score between T0 and T3.
- MEL-T01 superior to MEL-S01 as measured by the change in PHQ-9 score between T0 and T3.

Secondary hypotheses:

- In terms of a score change from T0 to T3,
MEL-T01 is superior to TAU,
and MEL-S01 is superior to TAU,
and MEL-T01 superior to MEL-S01 in:

- reducing depression symptoms as measured by quick inventory of depressive symptomatology (QIDS),

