3.7.4 Power and sample size

3.7.4.1 Power analysis

A power analysis was conducted to determine appropriate sample size for the study to detect a statistical difference between change scores for the primary hypothesis in a two tailed, repeated measures t-test. Assuming that our samples are independent and identically distributed with normal distribution (see [3.7.3](#)), we analyse the required sample size as follows:

- We conduct sample size analysis using G*Power 3.1.9.7
- We use a two-tailed t-test.
- Cohen (1988) suggests a small effect size is 0.20 and medium effect size is 0.50. As a point of comparison, a meta-analysis of internet-based treatments for adult depression have reached an average effect size of 0.41 (Anderson & Cuijpers, 2009). Meanwhile, Motter et al. (2016) found in their meta-analysis that computerised cognitive training had an effect size of 0.43 on depression symptom severity. Thus, we use an effect size $d = 0.40$.
- We use an alpha error probability of 0.0167 that corresponds to an alpha level of 0.05 with Bonferroni correction for the three primary endpoint tests.
- We use power of 0.80
- We allocate subjects equally to the three arms, leading to allocation ratio of 1:1:1

This leads to a total sample size of 133 per arm and with three arms this equals 399 subjects, which we round to **400 subjects** that we aim to have in T3.

Karyotaki et al. (2015) explored the dropout in self-guided web-based interventions for depression using different psychotherapeutic approaches. While their approach is based on psychotherapies, and ours on cognitive training, the medium of training is the same

(web-based), the intervention is self-guided, and they target people with depression. Karyotaki et al. found that in 10 RCTs 59% of the subjects dropped out before completing half the treatment modules.

Meanwhile, Torous et al. (2020) explored dropout rates for app interventions for depression. Considering publication bias, they found a dropout rate of 47.8%.

Considering the above, we assume a dropout rate of 50%. Thus, we aim to recruit up to 400 subjects / 0.50 = 800 subjects to begin the study.

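### The 18 secondary superiority contrasts have no multiplicity rule and no gate on PHQ-9, and the sections disagree on whether these scales are tested claims or supportive evidence

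*Combined protocol and SAP*

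**What the plan says.** **Hypotheses (3.1.6 and 3.5).** The secondary hypotheses open with "In terms of a score change from T0 to T3". They then state that MEL-T01 beats TAU, that MEL-S01 beats TAU, "and MEL-T01 superior to MEL-S01 in" six scales: QIDS, RRS, GAD-7, SDS, PVSS and WHO-5. Four more secondary hypotheses concern play-time dose and immersion. A separate exploratory tier follows.

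**Tests (3.7.3).** The section opens with "Primary and secondary objectives in this clinical study are to demonstrate a statistical difference on outcome measure mean change scores" and lists the same three arm pairs. Its test rule then narrows: "For primary endpoint evaluation (PHQ-9), we will conduct a one-tailed test for the arm pairs", at 0.05 with a Holm-Bonferroni first step of 0.05/3 = 0.0167.

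**Power (3.7.4.1).** The sample size uses 0.0167, described as "an alpha level of 0.05 with Bonferroni correction for the three primary endpoint tests".

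**Missing data (3.7.2).** The one analysis rule that names the secondary hypotheses says that their missing data are treated like the primary's.

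**Rationale (3.6.1).** QIDS is included to back up the PHQ-9 finding. The other scales are introduced as describing the range of depressive symptoms, mostly in tentative terms.

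No section gives the secondary tests an alpha, a sidedness, an order, a correction or a condition on PHQ-9.

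**The concern.** Three primary tests are corrected, while 18 contrasts stated in the same language of superiority have no rule. If neither device did anything, the trial would still quite often produce a nominally significant result on some scale, such as rumination, anxiety or well-being. Nothing in the plan says how such a result may be described.

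Two places are most exposed. The first is MEL-T01 against MEL-S01, on which section 3.6.2 rests its inference about cognitive training: this pair gets six further chances. The second is a negative PHQ-9 result, because no text prevents a positive QIDS or WHO-5 result from being reported as superiority in its own right.

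**Working it through.** **1. The plan's own figures.** 0.05/3 = 0.0167. With d = 0.40, two-sided alpha 0.0167 and 80% power, the exact noncentral t calculation gives 133 per arm (power 0.803), as stated in 3.7.4.1. So the correction was set for three tests. The secondary count is 6 scales x 3 pairs = 18, without the four dose and immersion hypotheses.

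**2. Independent tests, as a ceiling.**
- Each test at 0.05: 1 - 0.95^18 = 0.603.
- Each test at 0.0167: 1 - 0.9833^18 = 0.262.

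**3. Allowing for correlation.** The three contrasts share arms and the six scales are correlated. I simulated three independent arm means on six equally correlated scales under the global null. For each scale and pair, z = (mean of x - mean of y)/sqrt(2) in standardised units, and I counted replicates with any p-value below the cut. Arm size drops out under the null. The correlation is an assumption.

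| Correlation | One-tailed 0.05 | Two-tailed 0.05 | One-tailed 0.0167 within each scale |
|---|---|---|---|
| 0.3 | 0.48 | 0.50 | 0.21 |
| 0.5 | 0.41 | 0.44 | 0.18 |
| 0.7 | 0.33 | 0.35 | 0.14 |
| 0.8 | 0.29 | 0.31 | 0.12 |
| 0.95 | 0.20 | 0.21 | 0.08 |

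The last column stands for Holm within each scale: under the global null, Holm makes an error only if its first step does. The same calculation for the three PHQ-9 tests gives 0.045.

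The two-tailed column counts errors in either direction. At correlation 0.5, the part of its 0.44 in which at least one test wrongly favours the hypothesised arm is 0.25.

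**4. MEL-T01 against MEL-S01 only.** Six one-tailed tests at 0.05 give 0.22, 0.19 and 0.13 at correlations 0.3, 0.5 and 0.8.

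**5. The missing gate.** Suppose that all three PHQ-9 tests fail at 0.0167 under the global null, and that PHQ-9 has the same correlation with the other scales. The chance of at least one secondary result below one-tailed 0.05 is then 0.46, 0.39 and 0.26 at correlations 0.3, 0.5 and 0.8.

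**6. Testing a gated remedy.** Let a pair's secondaries be tested only after its PHQ-9 test is rejected, with Holm over six scales at 0.0167.
- *PHQ-9 tests fixed at 0.0167.* If a pair's PHQ-9 null is true, the gate limits its error to 0.0167. If it is false, Holm over the secondaries does. Three pairs give at most 3 x 0.0167 = 0.05.
- *Holm step-up kept on PHQ-9.* Let both devices beat TAU on PHQ-9 equally, with no secondary effects. The two TAU pairs can each spend 0.0167 on secondaries, while MEL-T01 against MEL-S01 on PHQ-9 can be tested at 0.05. The bound is 2 x 0.0167 + 0.05 = 0.083. In simulation with 133 per arm and d = 0.40, the error is 0.070, 0.066 and 0.057 at correlations 0.3, 0.5 and 0.8. With d = 0.80 it is 0.075 at correlation 0.5.

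**The case against.** The best defence is that the secondary scales were never meant to carry claims. Section 3.6.1 gives QIDS a corroborating role and speaks tentatively of the others. The main objective in 3.5 and the benefit rule in 3.7.5.1 rest on PHQ-9 alone. Leaving secondary scales outside alpha control is accepted practice when they are labelled supportive.

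Much of this stands. A reader might infer that the plan designates these 18 tests as confirmatory, or that it lets QIDS or WHO-5 rescue a failed PHQ-9. The documents support neither: they do not use that label, and they define no route to trial success through a secondary scale. The exposure is in what may be reported.

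A reader might also infer that each secondary test is run at 0.05. That is not stated. The 0.05 sits in the same PHQ-9 item as the Holm correction, so either it does not reach the secondaries or the correction over three pairs arguably comes with it. This is why two sets of figures are given. Sidedness is no clearer: 3.7.3 specifies one-tailed tests under a two-sided alternative, and 3.7.4.1 uses a two-tailed test.

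The defence does not remove the conflict. Section 3.7.3 assigns both tiers the same aim, 3.5 words the hypotheses as superiority, and the separate exploratory tier shows that the secondaries were not meant to be exploratory.

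**Conclusion.** The concern holds as a gap and an inconsistency. The plan states 18 secondary superiority contrasts with no error control and no gate, while another section implies a supportive role.

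Under the global null, with assumed between-scale correlations of 0.3 to 0.8, the chance of at least one false claim is about 29% to 50% at 0.05 per test, and about 12% to 21% with 0.0167 carried over within each scale. The primary family is held to at most 5%, leaving the interim analysis aside. A single headline figure would overstate what is known, because the documents give neither the correlation nor the secondary alpha. The direction is secure: even at correlation 0.95 with the carried-over cut, the figure is 8%.

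It would be wrong to conclude that the PHQ-9 inference is affected. It is not, so this should be corrected but does not threaten the primary result.

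**What to change.** **Preferred.** In 3.1.6, 3.5 and 3.7.3, label the six secondary scales as supportive of PHQ-9. State that they will be reported as estimates with confidence intervals and unadjusted p-values, and that no superiority claim will be made from them. Replace the superiority wording in the secondary hypotheses, limit the opening aim of 3.7.3 to the primary objective, and state the status of the four dose and immersion hypotheses.

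**If formal secondary claims are wanted.** Allow them for an arm pair only after that pair's PHQ-9 hypothesis is rejected, using Holm over the six scales at a total of 0.0167 and a stated sidedness. Then choose one of two rules for PHQ-9:
- hold each PHQ-9 test at a fixed 0.0167; or
- pass a pair's alpha to the other PHQ-9 tests only after all six of that pair's secondaries are rejected.

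Do not add the gate while leaving the present Holm step-up on PHQ-9 unchanged, since that raises the family-wise error to about 0.06 to 0.08.

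**Cost.** Wording only, with no extra subjects or data. Some nominally significant secondary results could no longer be called superiority. The fixed-0.0167 option also gives up Holm's small power gain on PHQ-9. The text should be settled before anyone sees unblinded secondary results, or the choice will look data-driven.
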